In summary, following smokers during the first two weeks of a smoking cessation attempt provides important laboratory-to-clinical translational benefits. The use of a two week surrogate endpoint for measuring cessation outcomes is innovative and also resource efficient. The use of EMA to track smoking as well as stressor-smoking, stressor-affect and stressor-urge relationships is also innovative in the combination with laboratory measures. These data will allow us to directly examine if 1) our laboratory measures of negative affective response to stressors predict individual differences in stressor coupling with negative affect, urge, and smoking (AIM 2), 2) our laboratory measures predict smoking cessation outcomes across all smokers, regardless of medication group (AIM 3), 3) our laboratory measures differentially predict smoking cessation outcomes across combo NRT vs. placebo as would be expected if combo NRT reduces the influence of negative affect on smoking (AIM 4). To further evaluate AIM 4, we will also re-administer our laboratory cued threat task at 2 weeks post-quit to determine if combo NRT alters negative affective response to stressors and to test if this laboratory measure obtained during treatment mediates combo NRT effects (relative to placebo NRT with counseling) on smoking cessation outcome.

SPECIFIC AIMS

Neuroscience research with animal models implicates neuroadaptation in the stress response as a critical mechanism in the etiology of addiction across multiple classes of drugs including nicotine (22–24). Repeated homeostatic adjustments in the brain's stress systems due to chronic drug administration eventually lead to persistent compensatory adaptations in the structures involved in emotional response and its regulation. Among smokers, these stress neuroadaptations result in dysregulated negative affect when nicotine-deprived and provide the strong motivational press for further smoking that manifests as urge and increased risk for relapse (21,25).

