1.1: Nicotine deprived smokers will display selectively increased negative affect measured via startle potentiation during uncertain (vs. certain) threat relative to non-deprived smokers.

AIM 2: Examine the impact of stress neuroadaptation on negative affect, smoking urge, and smoking in response to stressors. Laboratory startle potentiation measures of stress neuroadaptation will predict ecological momentary assessment measures of:

2.1 ...overall levels of negative affect and urge
2.2 ...within-smoker covariation (i.e., coupling) of episodic stressors with negative affect, urge, and smoking (i.e., stressor-induced negative affect, urge and smoking).

AIM 3: Examine the impact of this stress neuroadaptation on smoking during the first two weeks of smoking cessation.

3.1: Laboratory startle potentiation measures of stress neuroadaptation will predict overall smoking during the first two weeks post-quit as well as measures of point prevalence abstinence and continuous abstinence measured at 2 weeks post-quit.

AIM 4: Determine if treatment of withdrawal via NRT reduces the influence of stress neuroadaptation.

4.1: Combo NRT with counseling (vs. placebo NRT with counseling) will reduce startle potentiation measures obtained at one week post-quit.

4.2: The effect of combo NRT (vs. placebo NRT with counseling) on smoking and related outcome measures will be mediated by change in startle potentiation measures from pre-quit to post-quit.

4.3: Treatment of withdrawal symptoms via combo NRT will attenuate the predictive strength of pre-quit startle potentiation measures with respect to overall levels of negative affect, urge, and smoking and stressor-induced negative affect, urge, and smoking.

RESEARCH DESIGN AND METHODS

C1: BRIEF OVERVIEW

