Three hundred participants (identified as heavy smokers) will be recruited. All participants will complete an experimental cued threat task (No shock/Predictable shock/Unpredictable shock, or NPU, as described above) designed to assess the affective components (fear, anxiety) of their response to stressors in the laboratory to test for stress neuroadaptation resulting from chronic smoking. Participants will complete the task twice in two separate experimental sessions on separate days. The first time they will be either nicotine deprived and/or non-deprived (counterbalanced). Participants are randomly assigned to one of two treatments (Combo NRT with counseling or placebo NRT with counseling) and schedule a quit date. All participants will provide 3 weeks (1 week pre-quit; 2 weeks post-quit) of 4x daily, real-time report of stressors, affective state, urge to smoke, actual cigarette use, and study medication adherence. Participants return to the laboratory at 2 weeks post-quit. At this follow-up visit, stressor exposure, affective status, withdrawal symptoms, smoking urge, tobacco use, and medication adherence will be measured. Biological confirmation (CO measurement) of recent smoking is also obtained. At the 2 week post quit visit, they complete the second administration of the experimental cued threat task.

C2: GENERAL METHODS AND MEASURES

This section provides detail on the general methods and measures in this application. A separate section (C3) details the experimental cued threat task.

C2.1: Participants. Three hundred smokers (approximately 1/3 female as represented in the Madison smoking community) will be recruited. Inclusion criteria include cigarette use ≥ 10 cigarettes/day \geq two years, smoke within the first 30 minutes of waking up, expired air carbon monoxide (CO) level ≥ 6 ppm, self-reported motivation to quit smoking, ability to read and write English, and an agreement to respond to EMA prompts throughout the day for three weeks. Health screening will ensure that participants can safely use the nicotine patch and lozenge. Specifically, participants will be excluded for FDA contraindications for NRT (e.g., no uncontrolled hypertension, recent myocardial infarction, diabetes, heart disease, asthma, stomach ulcers). All women of child-bearing potential will be required to agree to use an approved method of birth control to prevent pregnancy during the course of the study.

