All participants report some demographic information, their current affective state (Positive and Negative Affect Scales-PANAS (120), provide information on a broad-band personality measure (Brief Multidimensional Personality Questionnaire- bMPQ); (121) and supplemental measures of trait affectivity relevant to individual differences in anxiety including the Intolerance of Uncertainty Inventory, (122), and the Anxiety Sensitivity Inventory (123). Individual differences in depressive symptoms will also be recorded Center for Epidemiologic Studies Depression Scale Revised (CESD-R; 125) and the Depression Anxiety Stress Scale-21 (DASS-21).

These measures are available to serve as covariates to increase power to test for focal effects on relevant outcome measures. They are also available as possible individual difference moderators in supplemental analyses. After completing the self-report measures, participants schedule their first experimental session. Participants are randomized to either a nicotine deprived or non-deprived condition and instructed to abstain from all nicotine containing products for 24 hours prior to their nicotine deprived session or to continue their normal pattern of smoking prior to their non-deprived session.

Finally, participants receive brief cessation counselling, schedule their experimental visits and quit date, and are provided with verbal and written instructions about the 3-week daily EMA survey that begins one week before their quit date.

C2.3: Laboratory Experimental Session(s)

All participants complete the cued threat task (NPU; see section C3 below) in each of two separate experimental sessions. Their first session is either nicotine deprived and non-deprived in a counterbalanced order, the final is 2 weeks post-quit. The deprived group completes their first experimental session the day after the start of their quit attempt, and the non-deprived group completes it before the start of their quit attempt. Data across the two experimental sessions will be used to provide sensitive within-subjects tests of deprivation effects on startle potentiation measures of stress neuroadaptation (Aim 1) and to address all subsequent Aims (2-4).

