our and other laboratories, shock intensity during these tasks is calibrated to each participant's individual sensitivity threshold, which is assessed prior to the main task during each experimental session to reduce individual differences (34,62,64,135). Startle potentiation is the primary dependent measure of affective response. As reviewed earlier, basic affective neuroscience research has indicated that startle potentiation is a sensitive and selective index of the neurobiological substrates of fear and anxiety, respectively, during conditions of certain vs. uncertain threat (30,72,74).

Participants in the non-deprived group will complete the task once pre-quit; in the deprived group, immediately post-quit, while both groups will also complete the task 2 weeks post-quit (counterbalanced) in separate experimental sessions separated by approximately two weeks. Task details are provided below. Task order within an experimental session is counterbalanced across all participants. We have preliminary data among 23 smokers in the context of an ongoing study that verify that smokers will tolerate multiple administrations across separate days of similar cued threat tasks.

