Analysis of Treatment Outcome (AIMS 3, 4.1, 4.2): Number of cigarettes smoked (17,18), point prevalence abstinence and continuous abstinence (as defined by the SRNT Workgroup on Biochemical Confirmation (149)) will be analyzed in Generalized Linear Models with time (1 week vs. 2 weeks) as a within subject factor. Startle potentiation measures from the cued threat task will be included as quantitative regressors to test if our laboratory stress neuroadaptation biomarkers predict treatment outcome measures (Aim 3). As above, treatment condition can be included as a moderating between subject factor to test if the relationships between startle potentiation and treatment outcome differ generally when withdrawal symptoms. Finally, mediation analyses can be conducted to determine if NRT alters startle potentiation measures at one-week post quit (AIM 4.1) and the startle potentiation measures mediate NRT effects on smoking outcome measures (AIM 4.2).

C4.3: Sample Size Justification. The primary analyses of startle potentiation will be accomplished within the General Linear Model (GLM). The analyses of smokers test for a two way interaction between Deprivation Status and Threat Uncertainty. Cohen (150) defines 0.15 for the squared multiple partial correlation as a medium effect size for GLM analyses. To be conservative, we powered our experiments to provide 90% power to detect a somewhat smaller (0.10) effect size. N=142 will provide 90% power to detect a squared multiple partial correlation of 0.10 for the interaction in a model that contains the two main effects and interaction based on formula provided by Cohen. We then increased this sample size to the round 150 within each Treatment Group to provide flexibility to counterbalance all relevant additional task factors. This yields N=300 across the two Treatment Groups. Given that the multilevel models that will be used to test questions about the EMA data are essentially GLMs fit at two separate levels of analysis (occasion and person levels), N=150 within each Treatment Group will provide comparable high power to test person-level predictors of both occasion-level intercepts (e.g., overall smoking, levels of negative affect) and stressor coefficients (e.g., stress-instigated smoking or negative affect).

DATA AND RECORD KEEPING

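### Startle on study medication is scheduled only at 2 weeks, after the smoking outcomes are complete, so Aim 4.2 cannot test mediation; the aims and analysis text say one week

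*Combined protocol and SAP*

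**What the plan says.** **One-week passages.** Aim 4.1 predicts that combo NRT "will reduce startle potentiation measures obtained at one week post-quit". Section C2.4.1 also places the on-treatment task at one week. The Analysis of Treatment Outcome paragraph tests startle "measures at one-week post quit (AIM 4.1) and the startle potentiation measures mediate NRT effects on smoking outcome measures (AIM 4.2"), and models smoking "with time (1 week vs. 2 weeks) as a within subject factor". The risk section (part A, study medications) mentions a 1-week laboratory visit, but only for asking about side effects.

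**Two-week passages.** The end of section A5 plans to "re-administer our laboratory cued threat task at 2 weeks post-quit". Section C1 says: "At the 2 week post quit visit, they complete the second administration of the experimental cued threat task". Sections C2.3, C2.6 and C3 agree: two sessions, the second at 2 weeks.

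**The change score.** Aim 4.2 says the NRT effect on smoking "will be mediated by change in startle potentiation measures from pre-quit to post-quit". Section C2.3 states: "The deprived group completes their first experimental session the day after the start of their quit attempt". Section C3 places that session "in the deprived group, immediately post-quit, while both groups will also complete the task 2 weeks post-quit". Section C2.4.1 nevertheless labels the deprived session pre-quit.

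**Order within and after visits.** Under C2.3, time of last cigarette and CO are taken on arrival, before the task, and medication is handed out after the first task. C2.4 makes the 2-week visit the last contact, and C2.6.1 rules out later outcomes on grounds of resources.

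**The concern.** A mediation claim needs the mediator to be measured before the outcome it is said to influence. On the scheduled procedures, the only startle value obtained on NRT or placebo comes at the end of the outcome window, so an association between that value and smoking can run in either direction.

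Reverse influence is plausible on the trial's own reasoning. Section A3 and Aim 1.1 hold that nicotine deprivation raises startle under uncertain threat, and smoking during the quit attempt changes deprivation. On that reasoning smoking lowers startle, which would hide a real startle pathway. If smoking raised startle instead, the same analysis could show mediation where there is none.

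Section C2.6 says the 2-week task allows mediation to be tested, so a null or a positive Aim 4.2 result could be read as evidence about mechanism that the data cannot give. In addition, Aim 4.2's baseline does not exist as worded for the deprived group, and the analysis text names a measurement that the procedures do not schedule.

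**Working it through.** The plan gives no figure for Aim 4.2, so there is none to reproduce. The check is a timeline, followed by an illustration.

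**1. Timeline (quit day = 0, outcome window 14 days).**
- Task at 2 weeks, as the procedures say: 14 − 14 = 0 outcome days follow the mediator.
- Task at one week, as Aim 4.1, C2.4.1 and the analysis text say: 14 − 7 = 7 days follow it, so week-2 smoking could serve as a later outcome.
- Pre-quit task values: one in the non-deprived group, none in the deprived group.

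The discrepancy therefore decides whether any outcome follows the mediator.

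**2. Masking: a true pathway, with smoking lowering startle.** All effect sizes are assumptions. There are 150 per arm, two-sided alpha is 0.05, T = NRT and e = independent standard normal error.
- Early startle: M1 = −0.4T + e
- Smoking: S = −0.3T + 0.3·M1 + e
- 2-week startle: M2 = k·M1 − 0.4(1−k)T + g·S + √(1−k²)·e

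Here k is the stability of startle and g the feedback from smoking. With g = 0 the NRT effect on M2 stays at 0.4 SD. The joint test requires both T on M and M on S given T to be significant, in the hypothesised direction.

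The mechanism can be checked by hand. Within arms, cov(M2, S) = 0.3k + g(1 + 0.3²) = 0.3k + 1.09g. At k = 0.6:
- g = 0: 0.18
- g = −0.1: 0.18 − 0.109 = 0.071
- g = −0.2: 0.18 − 0.218 = −0.038, so the sign reverses

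Simulated detection (M1 detects mediation in about 93% throughout):

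| Feedback g | M2 joint test, k = 0.6 | Range over k = 0.4 to 0.8 | Randomised T on M2, k = 0.6 |
|---|---|---|---|
| 0 | 79% | 48% to 91% | 93% |
| −0.1 | 19% | 4% to 54% | 88% |
| −0.2 | under 1% | 0% to 5% | 79% |

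Late timing alone costs 93 − 91 = 2 to 93 − 48 = 45 points. The rest of the loss needs feedback.

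**3. False mediation: no true pathway.** S = −dT + e and M = gS + e, with d = 0.3 to 0.8 and g = ±0.2 to ±0.4. Joint significance occurs in about 7% to 73% of trials for either sign of g. Hand check at d = 0.5, g = 0.3: the effect of T on M is 0.15 in size, its SE is √1.09 × √(2/150) = 0.1206, and 0.15/0.1206 = 1.24. P(Z > 1.96 − 1.24) is about 24%, and the M–S test is almost always significant. The result falls in the hypothesised direction only if smoking raises startle. If smoking lowers startle that share is 0%, and the artefact reads as NRT raising startle.

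**4. Aim 4.1 with smoking as a covariate.** C2.4.1 allows, but does not require, covariates for first-week smoking and medication use, both of which NRT can affect. Assume no NRT effect on startle and a shared vulnerability loading 0.3 to 0.5 on smoking and on both startle sessions. Adjusting for session-1 startle and deprivation group only, type I error is about 4% to 6%. Adding smoking gives about 5% to 27%, with bias up to 0.16 SD.

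**The case against.** **Size and sign.** The feedback coefficients are not in the documents. With none, the 2-week measure still detects mediation in 79% of trials at stability 0.6. The direction suggested by A3 supports masking, not a false positive for the hypothesis. Both points stand: the simulations show what could happen, and the false-positive case is secondary. It is also fair that the illustration uses raw 2-week startle while Aim 4.2 uses change, but adjusting for a session-1 value makes the masking worse.

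**Which time point is meant.** If one week is intended, week-2 smoking would follow the mediator and much of the ordering problem would go. But no procedural section schedules a task then, and the 1-week visit in the risk section has none assigned.

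**The change score.** Every participant has a first session before medication, so a session-1 to session-2 change exists for all. That is right. What is missing is a pre-quit value for the deprived group, and the baseline state differs between groups.

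**Blinding and visit calendars.** C2.4 says staff are unblinded because the two arms need different visit calendars. If this means the treatment arms, the Aim 4.1 comparison carries a caveat of its own.

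**Weight.** The statistical section says mediation analyses can be done, and Aim 4.2 is not the powered analysis. This limits the importance of the point but does not remove it, since C2.6 presents the mediation test as something the design delivers.

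**Conclusion.** The concern holds and should be fixed. Three parts rest on the text alone: the one-week and two-week passages contradict each other; on the scheduled procedures none of the 14 outcome days follows the on-medication task; and the deprived group has no pre-quit startle value. As scheduled, Aim 4.2 can show that startle and smoking are associated at the end of treatment, not that startle carries the NRT effect.

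The size of the distortion depends on assumptions. At stability 0.6, detection of a real pathway falls from 93% with an early measure to 79% with late timing alone, and to 19% or lower once smoking lowers startle by a coefficient of 0.1 or more. Aim 4.1 is much less affected: the randomised comparison of 2-week startle keeps 79% to 93% power in the same settings, and a null there would be some evidence against the mechanism. The problem limits one secondary claim, not the trial as a whole.

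**What to change.** 1. Reconcile the task timing in Aim 4.1, C2.4.1, the risk section and the Analysis of Treatment Outcome paragraph with the scheduled 2-week session, and correct the pre-quit label on the deprived session.
2. Under Aim 4.2, report the relation of 2-week startle to smoking as an association and state that the time order does not support mediation. Define change as session 1 (before medication) to session 2, with deprivation group in the model.
3. For Aim 4.1, make the main estimate the randomised comparison of 2-week startle, adjusted only for session-1 startle and deprivation group. Report it for uncertain and certain threat, which C3.2 already scores separately. Keep any model with post-randomisation smoking or medication use as supplementary.

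These are wording and analysis-plan edits; no new visits, data or participants are needed. The cost is giving up a formal claim that startle mediates the NRT effect.

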C3.2: Psychophysiological Measurement. Startle potentiation is the primary dependent measure from the cued threat tasks. Acquisition and scoring of the eyeblink startle response will follow well-established procedures described in the Society for Psychophysiological Research guidelines paper (136). The startle response will be elicited by acoustic probes (50 ms, 105 dB white noise with near instantaneous rise time) and measured by recording electromyographic (EMG) activity in the orbicularis oculi muscle. Startle electromyographic activity will be sampled (2500 Hz) and filtered (500 Hz low-pass) online with Neuroscan Synamps II amplifiers. Offline processing includes high-pass filtering (28 Hz high-pass 4th order Butterworth filter), signal epoching (-50ms to 250ms relative to acoustic probe), rectification, and smoothing (30 Hz low-pass 4th order Butterworth filter). Peak eyeblink startle response is scored between 20-100 ms post-probe onset relative to mean 50 ms pre-probe baseline. Our laboratory has used these procedures in published research involving drug administration and deprivation for over a decade (33,34,58,64,86,137,138). Startle

potentiation scores are calculated as the increase in startle response during threat vs. no-threat conditions separately for certain and uncertain threat conditions.

We will also collect two secondary measures of affective response (corrugator electromyographic activity, and electroencephalography (EEG)) to measure facial display of affect and general arousal, respectively, in response to certain and uncertain threat cues. Participants will be prepared for recording by using AgAgCl sensors filled with a conductive gel and placed on various facial muscles (EMG includes orbicularis oculi – under left eye; corrugator –over left eyebrow) as well as on the scalp (EEG). Additionally two AgAgCl sensors will be placed on the forehead to act as ground and reference sensors. Acquisition and scoring of these measures will also follow well established procedures (139–141). Our laboratory has regularly collected these measures as part of a standard battery of peripheral psychophysiological measures of negative affective response (137,142–145).

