The Principal Investigator will refine existing protocols for assuring data accuracy and protocol compliance. Such protocols will include data verification and protocol compliance checks as well as other quality assurance procedures. The Principal Investigator will also be responsible for ensuring that the data for the project are securely stored, that storage is in compliance with University and federal regulations and that no unauthorized persons have access (electronic or physical) to any participant-identifiable data.

STATISTICAL CONSIDERATIONS

In this section, we outline general strategies for analysis of startle potentiation, EMA, and treatment outcome that are used to address our four aims. We sketch out clear exemplars of analysis options for this rich dataset. Of course, there are numerous supplemental analyses that space constraints prevent describing here.

ANALYSIS OF STARTLE POTENTIAION (AIM 1). The analysis of startle potentiation for Aims 1 & 1.1 across experimental tasks can be accomplished within very similar General Linear Models (GLMs). In each analysis, startle potentiation will be analyzed in a GLM with Threat Uncertainty (low vs. high probability for Threat Probability task; fixed vs. variable duration for Threat Duration task) as the focal within-subject factor.

Analysis of Aim 1.1 will use the full sample as a focal between-subject factor. Support for the stress neuroadaptation thesis following chronic tobacco use would be offered by a Smoking Group X Threat Uncertainty interaction with selectively greater startle potentiation among smokers in uncertain threat for each task. Analysis of Aim 1.2 will use both pre-quit sessions and include Deprivation Status (nicotine deprived vs. non-deprived) as a focal within subject factor. Support for the stress neuroadaptation thesis when nicotine deprived would be offered by a Deprivation Status X Threat Uncertainty interaction with selectively greater startle potentiation among deprived smokers in uncertain threat for each task.

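### The Aim 1 deprivation test does not fit the sessions described, and neither N=142 nor the slope-power claim in C4.3 can be reproduced from what is stated

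*Combined protocol and SAP*

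**What the plan says.** **Sample size (C4.3).** The powered test is named: "The analyses of smokers test for a two way interaction between Deprivation Status and Threat Uncertainty". The figure is "N=142 will provide 90% power to detect a squared multiple partial correlation of 0.10 for the interaction", in a model with the two main effects and the interaction, by a cited formula. N is then rounded to 150 per treatment group, 300 in total, to help counterbalancing. For the EMA models C4.3 adds that "N=150 within each Treatment Group will provide comparable high power to test person-level predictors of both occasion-level intercepts", and extends this to stressor coefficients.

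**Analysis (Statistical Considerations, Aim 1).** The model takes "Threat Uncertainty (low vs. high probability for Threat Probability task; fixed vs. variable duration for Threat Duration task) as the focal within-subject factor". The deprivation contrast is numbered 1.1 in the Specific Aims but 1.2 here: "Analysis of Aim 1.2 will use both pre-quit sessions and include Deprivation Status (nicotine deprived vs. non-deprived) as a focal within subject factor".

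**Sessions.** C2.2 randomises participants to a deprived or non-deprived condition. C2.3 gives one early session and a final one at 2 weeks post-quit, both with the NPU task. On timing it says "The deprived group completes their first experimental session the day after the start of their quit attempt", while the other group attends before quitting; C3 agrees. C2.6 places the second session during NRT or placebo use. Yet C2.3 also says "Data across the two experimental sessions will be used to provide sensitive within-subjects tests of deprivation effects". For the NPU task, C3.2 says startle "potentiation scores are calculated as the increase in startle response during threat vs. no-threat conditions separately for certain and uncertain threat conditions".

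**The concern.** This is the trial's only sample-size statement. Three things stop a reader from using it.

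- The test it powers cannot be run as the analysis section describes it, because no participant has two pre-quit sessions and the two tasks named there are not the task given.
- The inputs behind 142 are incomplete.
- The claim for stressor slopes carries a GLM figure over to person-specific coefficients, which are estimated with error.

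Without a settled test and stated inputs, a null result on Aim 1 or on stressor coupling cannot be judged against a known detectable effect.

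**Working it through.** **1. Sessions side by side.** The analysis section needs a deprived and a non-deprived pre-quit session in the same person. C2.3 and C3 supply only one early session per person. For the deprived group that session already falls after quitting starts, and no session is planned in their normal smoking state. The only within-person pair is the early session against the 2-week session. That pair differs in study medication, in time since quitting and in task repetition, as well as in deprivation. Session 1 itself is free of study medication: C2.3 hands out NRT or placebo after the task.

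**2. Trying to reproduce 142.** Stated inputs: power 90%, partial R² 0.10, three model terms. Deprivation has two levels. Threat uncertainty has two, both in the analysis section and in the C3.2 scoring. So numerator df = (2−1)(2−1) = 1. Alpha and sidedness are not stated; I assume two-sided 5%.

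Method: noncentral F, f² = R²/(1−R²) = 0.10/0.90 = 0.111, λ = f²·N, error df = N−4.

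- Large-sample: 10.51/0.111 = 94.6. Exact: N=97 (90.1% power).
- N=142 gives 97.6% power; N=150 gives 98.2%.
- One-sided 5%: N=79.
- 0.10 read as f², 1 df: N=108.
- R² 0.10, 3 df: N=132.
- f² = 0.10, 3 df: 14.17/0.10 = 141.7 large-sample, 146 exact.
- R² 0.10, 1 df, alpha 0.01: N=138. The alpha at which N=142 gives exactly 90% is 0.0083.

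At 5%, 142 does not follow from the test that C4.3 names.

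**3. What 0.10 means in each design.** Take the uncertain-minus-certain difference score.

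- Within subjects, R² 0.10 is d_z = √0.111 = 0.333.
- Between groups, R² 0.10 is d = 2√0.111 = 0.667.

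If 0.10 was meant within subjects, the same raw effect tested between groups is d = 0.333·√(2(1−ρ)). Here ρ is the correlation of the score between sessions, which the documents do not give. Between-group R² = d²/(d²+4).

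| Assumed ρ | d | Between-group R² | Power at N=300 | N for 90% |
|---|---|---|---|---|
| 0 | 0.471 | 0.053 | 98% | 190 |
| 0.3 | 0.394 | 0.037 | 93% | 272 |
| 0.5 | 0.333 | 0.027 | 82% | 380 |
| 0.7 | 0.258 | 0.016 | 61% | 632 |

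**4. Detectable effect for the test the design supports** (between groups, session 1, 1 df, two-sided 5%, 90% power). At N=300, f² = 0.0353, so R² = 0.0353/1.0353 = 0.034. With an assumed 15% or 20% unusable (N=255 or 240) it is 0.040 or 0.042.

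**5. Stressor slopes.** As an approximation, observed R² = 0.10 × slope reliability, with one predictor, error df N−2 and two-sided 5%. The reliabilities are assumed.

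| Reliability | N=300 pooled | N=150, one arm |
|---|---|---|
| 0.7 | 99.7% | 92% |
| 0.5 | 98% | 80% |
| 0.3 | 86% | 57% |

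Power of 90% needs reliability of about 0.34 at N=300 and 0.66 at N=150.

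**The case against.** **On 142.** A reader might infer from 97 against 142 that the plan miscalculated. The documents do not support that. The cited formula is not reproduced in them, alpha is not stated, and 3 df with f² = 0.10 comes to 141.7. For the named test at 5% the gap is also conservative. What stands is a reporting gap: that 3-df reading tests the whole model, not the interaction named.

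**On N=300.** A reader might infer that the sample is safe, since between-group R² 0.10 has over 99.9% power with 300. A reader might equally take the 61% above as proof that it is too small. Neither follows. The documents do not say which design 0.10 refers to and give no session correlation.

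**On the arms.** Because C4.3 sizes each treatment group, one might infer that Aim 1 is tested within one arm. The Aim 1 analysis text does not say so.

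**On slopes.** The plan uses multilevel models, so the two-stage figures are only illustrative. They also assume that 0.10 is the effect on error-free slopes. The Aim 2 analysis is not split by treatment, so the pooled column is the relevant one there. The one-arm column matters because C4.3 makes its claim for each treatment group. The claim is unsupported, not shown to be false.

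**Conclusion.** The concern holds as a mismatch between test and design, plus missing inputs. The within-subject test over two pre-quit sessions does not exist in the trial described, and a within-person contrast across the two actual sessions does not isolate deprivation. The figure of 142 cannot be reproduced from the text: the named 1-df interaction needs 97 at an assumed two-sided 5%. The adequacy of 300 is open until the meaning of 0.10 is fixed; if it was meant within subjects, between-group power runs from about 98% down to 61% over assumed correlations of 0 to 0.7. Comparable high power for stressor coefficients has no stated slope variance, stressor frequency or reliability behind it. Alpha, sidedness, session correlations, data loss and reliabilities are my assumptions, not the plan's.

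**What to change.** 1. Reconcile the Aim 1 analysis text with C2.3, C2.6 and C3. The design described supports Deprivation Status as a between-subject factor on session-1 data from all participants, with NPU certain versus uncertain threat as the within-subject factor. Remove the references to two pre-quit sessions and to tasks not given, and correct the within-subjects sentence in C2.3.
2. Restate C4.3 for that test with alpha, sidedness, 1 numerator df and the effect metric (partial R² or f²). In place of N=142, give the between-group partial R² detectable at 90% power: about 0.034 at N=300 and two-sided 5%, or 0.040 to 0.042 with 15–20% unusable. State the allowance used; it should cover deprived participants discontinued after failing twice to abstain (C2.3).
3. Say whether 0.10 was meant within or between subjects, and that the adequacy of N=300 depends on it.
4. Replace the comparable-power sentence with one statement for person-level intercepts and one for stressor slopes. Give the slope figures over a stated reliability range, labelled as an approximation, at pooled N=300 for Aim 2 and at N=150 for any within-arm claim.

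The cost is the Aim 1 model text, one sentence in C2.3 and one paragraph in C4.3, with no change in enrolment. The downside is that the stated power becomes less favourable and conditional on assumptions.
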